**Method of Allocation** 

In the phase II component, participants with *T. trichiura* infection (confirmed by Kato-Katz technique in a fresh stool sample) will be enrolled in a sequential manner per weight group in order to administer the desired dose, starting from 300-391  $\mu$ g/kg ivermectin. Participants in the phase II trial will be stratified in different weight groups: Group 1 (23-<30 kg) 38 participants, group 2 (30-45 kg) 38 participants and group 3 (15-23 kg) 50 participants in order to gradually increase the dose of ivermectin in the FDC. Then, participants will be allocated by simple randomization to one of the three study arms (ALB, FDCx1 and FDCx3).

In the phase III component, allocation of participants to study arms will be done by block randomization and stratified by STH species. We will ensure balanced allocation to the three arms in the three study countries. Treatment allocation for each study participant will be concealed in opaque sealed envelopes that will be opened only after enrolment. Study participants will be assigned a unique study number linked to the allocated treatment group. The allocation ratio for the three study arms will be 1:1:1.

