3.3 Treatment

Phase II component

Participants will be randomly allocated with unequal probability to receive either:

Treatment Arm 1: Single dose of a tablet of ALB

Treatment Arm 2: Single dose of a tablet of FDC

Treatment Arm 3: Daily dose of a tablet of FDC for 3 days.

and will be recruited by μ g/Kg of IVM to be received in a sequential manner starting from Group 1 through to Group 3 as shown below:

- Group 1: receiving 300-391 μg/Kg or ALB 400mg- 38 participants (body weight: 23-<30 Kg) will be recruited in this group. (FDC 400mg-9mg).
- Group 2: receiving 400-600 µg/Kg or ALB 400mg− 38 participants (body weight: 30-45 Kg) will be recruited in this group. (Participants <45 kg: FDC of 400mg ALB-9mg IVM, participants ≥45 kg: FDC of 400mg ALB-18mg IVM).
- Group 3: receiving 391-600 μg/Kg or ALB 400mg- 50 participants (body weight: 15-23 Kg) will be recruited in this group. (FDC 400mg-9mg).

Phase III Component

Participants will be randomly allocated with unequal probability (Arm 1 p=0.2, Arm2 p=0.4, Arm3 p=0.4), according to the specific expected cure rate by specie, to receive either:

Treatment Arm 1: Single dose of a tablet of ALB 400 mg (active control arm).

- Treatment Arm 2: Single dose of a tablet of FDC 400mg-18mg or 400mg-9mg.
 - For participants <45 kg of body weight at baseline: FDC of 400mg ALB-9mg IVM.

◦ For participants ≥45 kg of body weight at baseline: FDC of 400mg ALB-18mg IVM.

Treatment Arm 3: Daily dose of a tablet of FDC 400mg-18mg or 400mg-9mg for 3 days.

- For participants <45 kg of body weight at baseline: FDC of 400mg ALB-9mg IVM.
- For participants ≥45 kg of body weight at baseline: FDC of 400mg ALB-18mg IVM.

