3.4 Randomisation

In the phase II component, participants with *T. trichiura* infection (confirmed by Kato-Katz technique in a fresh stool sample) will be enrolled in a sequential manner per weight group in order to administer the desired dose, starting from 300-391 μ g/kg ivermectin. Participants in the phase II trial will be stratified in different weight groups: Group 1 (23-<30 kg) 38 participants, group 2 (30-45 kg) 38 participants and group 3 (15-23 kg) 50 participants in order to gradually increase the dose of ivermectin in the FDC. Then, participants will be allocated by simple randomization to one of the three study arms with unequal probability (ALB: p=0.2, n=26; FDCx1: p=0.4, n=50; FDCx3: p=0.4, n=50) In the phase III component, allocation of participants to study arms will be done by block randomization and stratified by STH species. We will ensure balanced allocation to the three arms in the three study countries. Treatment allocation for each study participant will be concealed in opaque sealed envelopes that will be opened only after enrolment. Study participants will be assigned a unique study number linked to the allocated treatment group. Participants will be randomly allocated with unequal probability, according to the specific expected cure rate of each species.

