3.6 Study stopping guidance

The following stopping rules will apply at relevant key instances in the ALIVE study:

- **ISGIODAI** Barcelona Institute for Global Health
 - The occurrence of ≥1 serious adverse reaction (where causality is at least possible) or SUSAR in any of the weight groups in the Phase II will result in suspension of dose escalation in the FDC arm pending review by the DSMB (keeping in mind the sequential recruitment strategy in phase II).
 - 2. The occurrence of ≥2 serious adverse reactions or SUSARs at the end of phase II will result in suspension of progress to phase III pending review by the DSMB.

Overall the occurrence of serious adverse reactions or suspected unexpected serious adverse reactions in 2% of the study populations at interim analysis (50% recruitment) will result in suspension of further dosing of the Investigational Product pending review by the DSMB. This is equivalent to 12 safety events which meet these criteria in 612 participants recruited at the point of the interim analysis.

Table 3. Sample size and power calculation according to the expected efficacy (Cure Rate) of the different treatment arms

Comparison Trichuris trichiura	Target Power	Actual Power	Sample Size	Expected Cure Rate	Overall Alpha	Bonferroni adjusted Alpha
ALB vs IVM-ALB vs (IVM-ALB)x3 IVM-ALB vs (IVM-ALB)x3	80% 80% 80%	91% 100% 80%	116 223 223	23.7% 43.7% 59%	0.05 0.05 0.05	0.0167 0.0167 0.0167
Strongyloides stercoralis ALB vs IVM-ALB vs (IVM-ALB)x3	80% 80%	95% 100%	42 108 107	45% 79% 94%	0.05 0.05	0.0167 0.0167
IVM-ALB vs (IVM-ALB)x3 Hookworm ALB vs IVM-ALB vs (IVM-ALB)x3 IVM-ALB vs (IVM-ALB)x3	80% 80% 80% 80%	80% 82% 80%	91 91 99	79.5% 79.5% 95%	0.05 0.05 0.05 0.05	0.0167 0.0167 0.0167 0.0167

	Pł	nase II		PHASE III		PHASE II/III
		N total			N tota	al
		Phase			Phase	
Group	N	II ¹	Ν		III ¹	N total
Trichuris trichiura						
ALB	23	26	93		103	129
FDCx1	45	50	178		198	248
FDCx3	45	50	178		198	248
Total	113	126	449		499	625
Strongyloides.						
stercoralis						
ALB			42		47	47
FDCx1			108		120	120
FDCx3			107		119	119
Total		0	257		286	286
Hookworm						
ALB			91		101	101
FDCx1			91		101	101
FDCx3			99		110	110
Total		0	281		312	312
TOTAL		126			1097	1223

Table 4. Final sample size calculation taking into account 10% lost-to-follow-up

¹Calculated by inflating the sample size using considering 10% lost-to-follow-up

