5.5 Safety analysis

Safety analysis in the phase II corresponds to the primary outcome/endpoint, i.e, the frequency, type, severity and relationship to study drug for all adverse events and severe adverse events. For the safety analysis in phase III, the safety population will be used for the analysis and participants will be considered by arm and by both FDC arms pooled (overall) and by number of doses of FDC received to explore dose-responses.

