5.5.1 Adverse events

All AEs will be coded using the latest version of MedDRA at the time of the database lock. The actual version of the MedDRA coding dictionary used will be noted in the AE tables and listings.

Treatment-emergent adverse events (TEAEs) are defined as adverse events that occur or worsen on or after the first dose of study treatment.

The severity of the adverse events is assessed by the investigator as mild, moderate, or severe. The relationship to the study drug is determined by the investigator as definite, probably, possibly, unlikely, or unrelated. The categories "unrelated" and "unlikely" will be mapped to "unrelated", the categories "possibly", "probably" and "definite" will be mapped to "related".

An adverse event is considered a serious adverse event (SAE) if it results in any of the following outcomes: 1) results in death, 2) is a life-threatening adverse event, 3) requires hospitalization or prolongation of existing hospitalization, 4) results in a persistent or significant disability/incapacity or substantial disruption of the ability to conduct normal life functions, or 5) a congenital anomaly/birth defect.

An overall summary of TEAEs will be presented showing the number and percentage of participants with: any TEAE, any study drug-related TEAE, any severe TEAE, any treatment-emergent SAE, any study drug-related treatment-emergent SAE, any TEAE leading to study discontinuation, and any TEAE leading to death.

The following TEAEs will be summarized as frequency and percentage of participants by SOC and PT:

- TEAEs
- TEAEs by descending PT
- Severe TEAEs
- Study drug-related TEAEs
- Treatment-emergent SAE
- Study drug-related treatment-emergent SAE
- TEAEs leading to study discontinuation

All adverse events for each patient, including the same event on multiple occasions, will be listed, indicating the preferred term.

Drug-related TEAEs will be analysed using ordinal logistic regression with the untoward effect classified as absent, mild, moderate, or severe and the factorial treatment regimens (without interaction term) as predictor variables. For a count outcome such as the number of TEAEs or treatment-emergent SAEs incidence rate ratio (IRR) and its 95% CI will be computed using Poisson or Negative binomial regression.

The following by-participant listings will be provided:

- AEs
- SAEs
- TEAEs leading to study drug withdrawal
- TEAEs leading to study drug interruption
- TEAEs leading to study discontinuation

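### If Phase III uses the species-specific allocation ratios of SAP 3.4 and Table 4, the pooled arms differ in species mix by design, and the safety models do not adjust for it

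*SAP*

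**What the plan says.** **Allocation.** SAP 3.4 says of Phase III that "allocation of participants to study arms will be done by block randomization and stratified by STH species", and ends with "Participants will be randomly allocated with unequal probability, according to the specific expected cure rate of each species". The Protocol synopsis and Protocol 6.1.2 also tie the unequal probabilities to species. The planned cell sizes are in the SAP table titled "Table 4. Final sample size calculation taking into account 10% lost-to-follow-up" (Table 2 in Protocol 9.2).

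Two other passages give one ratio for all species. SAP 3.3 says "Participants will be randomly allocated with unequal probability (Arm 1 p=0.2, Arm2 p=0.4, Arm3 p=0.4". Protocol 4.1, under Method of Allocation, says "The allocation ratio for the three study arms will be 1:1:1". SAP 3.4 adds: "We will ensure balanced allocation to the three arms in the three study countries". Protocol 6.3 has each institution randomise separately.

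**Safety analysis.** In SAP 5.5 the Phase III "participants will be considered by arm and by both FDC arms pooled (overall"), and also by number of FDC doses received. In SAP 5.5.1 the ordinal logistic model for drug-related events takes "the factorial treatment regimens (without interaction term) as predictor variables". The Poisson or negative binomial rate ratios name no covariate. Neither species nor site appears in any safety analysis. By contrast, efficacy is analysed one species at a time, with site controlled where numbers allow (SAP 5.4).

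**The concern.** When the allocation probability differs between strata, the arms are comparable within each stratum, but the pooled arms are not. An arm that takes a larger share of one stratum carries more of that stratum's background AE rate. Efficacy is protected from this because each species is analysed alone. Phase III safety pools the species, and nothing in the planned models removes the difference in mix. A larger sample does not help, because the imbalance comes from the ratios and not from chance.

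At stake is the Phase III safety comparison of FDC and FDCx3 with ALB, a secondary endpoint. A background difference between strata could make the combination look worse than ALB or better than ALB when the drugs do not differ. A background difference is plausible: Protocol 10.2 describes different species as prevalent at different sites, and under Protocol 6.3 and 8.3.3 unblinded site physicians grade severity and causality by judgement.

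**Working it through.** **Step 1. Reproduce the plan's arm totals.** Inputs are the Phase III cells of SAP Table 4.

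| Stratum | ALB | FDC | FDCx3 | Total | ALB share of stratum |
|---|---|---|---|---|---|
| T. trichiura | 103 | 198 | 198 | 499 | 20.6% |
| S. stercoralis | 47 | 120 | 119 | 286 | 16.4% |
| Hookworm | 101 | 101 | 110 | 312 | 32.4% |
| Sum | 251 | 419 | 427 | 1097 | |

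SAP 3.5 states 251 for ALB, 427 for FDC and 419 for FDCx3. The column sums reproduce these, with the two FDC labels swapped. The single ratios do not fit. 0.2/0.4/0.4 gives 1097 × 0.2 = 219 and 1097 × 0.4 = 439 per FDC arm. 1:1:1 gives 1097/3 = 366 per arm. The stated totals therefore match only species-specific ratios.

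**Step 2. Planned species mix of each arm** (cell divided by column sum).

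| Stratum | ALB | FDC | FDCx3 | FDC arms pooled (846) |
|---|---|---|---|---|
| T. trichiura | 41.0% | 47.3% | 46.4% | 46.8% |
| S. stercoralis | 18.7% | 28.6% | 27.9% | 28.3% |
| Hookworm | 40.2% | 24.1% | 25.8% | 24.9% |

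Under either single ratio the expected hookworm share is 312/1097 = 28.4% in every arm. With Phase II added (T. trichiura only), the hookworm shares are 101/277 = 36.5%, 101/469 = 21.5% and 110/477 = 23.1%.

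**Step 3. Bias with no drug effect.** Let r_T, r_S and r_H be the AE risks in the three strata. The expected crude difference, pooled FDC minus ALB, is the sum over strata of (share in FDC − share in ALB) × risk:

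0.058 r_T + 0.095 r_S − 0.153 r_H.

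If only hookworm differs from the other two strata, this is −0.153 × (r_H − r_other), or about 1.5 percentage points per 10-point difference. The factor is 0.161 for FDC alone and 0.145 for FDCx3 alone.

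**Step 4. Size under assumed risks.** The documents give no AE risk by species, so every risk below is an assumption. The last column is the two-sided 5% error of an unadjusted two-proportion test of pooled FDC (846) against ALB (251), from 200,000 simulated trials per row with no drug effect.

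| Assumed risk T / S / H | ALB | FDC pooled | Odds ratio | Crude error |
|---|---|---|---|---|
| 20 / 30 / 25% | 23.9% | 24.1% | 1.01 | about 5% |
| 25 / 25 / 20% | 23.0% | 23.8% | 1.04 | about 5% |
| 20 / 20 / 30% | 24.0% | 22.5% | 0.92 | about 8% |
| 20 / 20 / 40% | 28.0% | 25.0% | 0.86 | about 16% |
| 30 / 30 / 10% | 22.0% | 25.0% | 1.19 | about 16% |
| 10 / 10 / 30% | 18.0% | 15.0% | 0.80 | about 21% |

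In the first row the S. stercoralis and hookworm imbalances almost cancel.

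**Step 5. After adjustment.** A Cochran–Mantel–Haenszel test stratified by species, on the same scenarios, has an error of about 5% in every row.

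**The case against.** The strongest objection is that the imbalance is conditional. Under SAP 3.3 or Protocol 4.1 every arm has the same expected mix and the bias is zero. This stands, and it makes the allocation conflict the first thing to settle. It does not dispose of the point, because the stated arm totals fit only the species-specific ratios.

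A reader might infer four stronger things that the documents do not support:

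- **That the bias has a predictable direction.** The mix is predictable. The sign depends on AE risks that are not given, and the table shows both signs.
- **That site confounding is established.** No site-by-species counts are given, randomisation is separate by institution, and balance across countries is promised. Protocol 10.2 also reports high hookworm prevalence in both Ethiopia and Kenya. Site confounding can be neither shown nor excluded.
- **That a false-positive rate near 20% is to be expected.** It needs a threefold AE contrast. It also comes from a two-proportion test that the SAP does not plan; the SAP specifies tables, an ordinal model and rate ratios with confidence intervals. The test here only gauges the size.
- **That the safety comparison is not randomised.** It is randomised within strata. The fault is an unadjusted pooled summary.

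The Table 4 cells are also species targets. Protocol 4.2 counts a co-infected child under each infecting species, and neither document says which stratum allocates that child, so realised shares may differ from those in step 2.

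Finally, both documents promise to include relevant covariates, and Protocol 9.5.6 foresees exploratory work on confounders. The covariate sentences sit in the secondary efficacy sections (SAP 5.4.1, Protocol 9.5.3); the SAP's names only HIV, and the Protocol exploratory section specifies no safety adjustment.

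**Conclusion.** The point holds on one condition: that Phase III allocates by species-specific ratios, as SAP 3.4, Protocol 6.1.2, Table 4 and the stated arm totals indicate. The planned hookworm share is then 40% of ALB against 24% and 26% of the FDC arms, and the planned safety models leave any AE difference between species strata in the treatment estimate.

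The bias is about 0.15 of the AE difference between the hookworm stratum and the others, with unknown sign. It is negligible if the strata have similar or offsetting AE risks, and about 3 points if they differ by 20. These sizes rest on the Table 4 counts, on assumed AE risks, and on each child belonging to one stratum. This is a modest weakness of a secondary analysis. It is still worth correcting, because the correction is valid under whichever ratio is used and costs almost nothing.

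**What to change.** 1. Reconcile the Phase III allocation statements in the Protocol synopsis, Protocol 4.1 and 6.1.2, and SAP 3.3, 3.4 and Table 4, so that one rule is stated. Correct the swapped FDC and FDCx3 totals in SAP 3.5 and Protocol 9.2.
2. State which species stratum allocates a co-infected child, and use that stratum in the analysis.
3. In SAP 5.5.1, add the randomisation stratum (species) and site as factors in the ordinal logistic and the Poisson or negative binomial models. Site belongs there because randomisation is run separately by institution.
4. Beside the crude AE tables, report Mantel–Haenszel risk differences weighted over the strata, for each FDC arm against ALB and for the pooled FDC arms against ALB.

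The cost is a few lines of text and two factors per model. Species and site are already recorded, so no new data are needed. If a single ratio turns out to have been used, the adjustment remains valid.

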3.5 Determination of sample size

Sample size was calculated based on available data from peer-review publications complemented with reasonable estimates of efficacy for those experimental groups that have not been previously tested. For these calculations, the efficacy of the control arm (Albendazole 400mg in a single dose), was obtained for *T. trichiura* and hookworms from a systematic review and meta-analysis where

temporary trends in efficacy (with the corresponding confidence intervals) were incorporated (Table 3)[4]. For the efficacy of the control arm against *S. stercoralis*, an alternative source was used [5], since the systematic review by *Moser et al* did not include this species; for that reason, a clinical trial that included an arm of Albendazole 400mg for 3 consecutive days was used, assuming a "best case scenario" for the efficacy of the control group; this estimated efficacy is also in the range of a systematic review assessing the efficacy of Albendazole at various (but not single) doses[5]. For the FDC at single dose, the calculations were based on the estimated efficacies (and their corresponding confidence intervals) in a systematic review that calculated the Relative Risks of cure of diverse drug regimens against Albendazole 400mg single dose (Table 3)[6,7]. For. *S. stercoralis*, the estimated efficacy of FDC was calculated based on a recent clinical trial using lvermectin single and multiple-dose regimens [8]. Finally, for the FDC in 3-dose regimens, considering its use in public health, deployment logistics in MDA campaigns and expected impact of the FDC, we estimated that an improvement of at least 15 percentage points would be the minimum improvement in efficacy to be demonstrated in order to make the FDCx3 regimen worth considering.

Sample size was calculated estimating the efficacy of the different experimental drug or combinations for each of the STH of interest [9,10], and gathering the individual samples sizes for the study. The sample size was calculated for pairwise comparisons of the expected Cure Rates for three study groups with an overall significance level of 5% adjusted for multiple tests by Bonferroni's correction, 80% power and inflated for 10% lost-to-follow-up.

The estimated total number of participants for the adaptive design is 1223 (*T. trichiura* 625, *S. stercoralis* 286 and hookworm 312). This sample size is powered to be able to measure efficacy for all three species in the phase III component. The sample size for the phase II component is 20% of the total participants for *T. trichiura* (126 participants). The remaining 80% of the *T. trichiura* participants will be randomised in the phase III component. Table 4 details the stratification of the participants per species with a 10% lost-to-follow-up.

The total number of participants to be included in this clinical trial is 1223 (126 in phase II and 1097 in phase III). Following randomisation, 251 participants will be allocated to the ALB treatment arm, 427 will be allocated to the FDC treatment arm and 419 in the FDCx3 treatment arm. Table 4 details the stratification of the participants per species with a 10% lost-to-follow-up.

The 10% lost-to-follow-up inflated sample sizes of the ALB-group for *T. trichiura, S. stercoralis* and hookworm are 129, 47 and 101 respectively, and the corresponding sample sizes of the individual experimental treatment groups are 248, 120, and 101 for FDC-group and 248, 119 and 110 for FDCx3-group. The corresponding powers of each of the tests are 91%, 100% and 80% to compare the CRs of *T. trichiura* in ALB vs FDC, ALB vs FDCx3 and FDC vs FDCx3 respectively; 95%, 100% and 80% to compare the CRs of hookworm respectively for ALB vs FDCx3 and FDC vs FDCx3 comparisons. We do not compare CRs of hookworm in ALB and FDC as they are known to be the same. These powers were computed assuming that the expected CRs for *T. trichiura* are 23.7%, 43.7% and 59% in the ALB, FDC and FDCx3 groups respectively; 45%, 79% and 94% for *S. stercoralis* and 79.5%, 79.5% and 95% for hookworm. **Table 3** and **Table 4** show the sample size calculation according to the expected Cure Rate for each drug and helminth of interest, and the resulting sample size inflated by 10% due to the estimated lost-to-follow-up. Assumptions used for the sample size calculations (e.g. expected CRs, lost-to-follow-up, etc) should be checked during the interim analysis.

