CRs of *S. stercoralis* in the above-mentioned comparisons and 82%, and 80% to compare the CRs of hookworm respectively for ALB vs FDCx3 and FDC vs FDCx3 comparisons. We do not compare CRs of hookworm in ALB and FDC as they are known to be the same. These powers were computed assuming that the expected CRs for *T. trichiura* are 23.7%, 43.7% and 59% in the ALB, FDC and FDCx3 groups respectively; 45%, 79% and 94% for *S. stercoralis* and 79.5%, 79.5% and 95% for hookworm. **Table 1** and **Table 2** show the sample size calculation according to the expected Cure Rate for each drug and helminth of interest, and the resulting sample size inflated by 10% due to the estimated lost-to-follow-up. Assumptions used for the sample size calculations (e.g. expected CRs, lost-to-follow-up, etc) should be checked during the interim analysis.

Table 1. Sample size and power calculation according to the expected efficacy (Cure Rate) of the different treatment arms

Comparison	Target Power	Actual Power	Sample Size	Expected Cure Rate	Overall Alpha	Bonferroni adjusted Alpha
Trichuris trichiura						
ALB			116	23.7%		
vs IVM-ALB	80%	91%	223	43.7%	0.05	0.0167
vs (IVM-ALB)x3	80%	100%	223	59%	0.05	0.0167
IVM-ALB vs (IVM-ALB)x3	80%	80%			0.05	0.0167
Strongyloides stercoralis						
ALB			42	45%		
vs IVM-ALB	80%	95%	108	79%	0.05	0.0167
vs (IVM-ALB)x3	80%	100%	107	94%	0.05	0.0167
IVM-ALB vs (IVM-ALB)x3	80%	80%			0.05	0.0167
Hookworm						
ALB			91	79.5%		
vs IVM-ALB	80%		91	79.5%	0.05	0.0167
vs (IVM-ALB)x3	80%	82%	99	95%	0.05	0.0167
IVM-ALB vs (IVM-ALB)x3	80%	80%			0.05	0.0167

Version 4.0 21st January 2022

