5.7 Interim analyses

Two interim analyses are planned: 1) after the end of the phase II component for decision making to move to the phase III component; 2) after 50% of the study participants are enrolled. Regular evaluation of the safety data every 3 months will be performed by the DSMB. The study is designed as a superiority trial, so all tests will be two-sided and an overall significance level will be 0.05 In the interim efficacy analysis, the expense function alpha with the O'Brien-Fleming approach will be used to determine the type I error rate for each interim and final analysis.

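### SAP 3.5 attaches the S. stercoralis powers (95%, 100%, 80%) to hookworm, whose calculated power is about 80% for each of its two comparisons

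*SAP*

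**What the plan says.** SAP 3.5 gives inflated group sizes and expected cure rates for three species, then the power of each pairwise comparison. After the *T. trichiura* powers, the sentence continues with "95%, 100% and 80% to compare the CRs of hookworm respectively for ALB vs FDCx3 and FDC vs FDCx3 comparisons". The next sentence rules out a third hookworm comparison: "We do not compare CRs of hookworm in ALB and FDC as they are known to be the same". The paragraph attaches no power to *S. stercoralis*, although it gives that species' cure rates ("45%, 79% and 94% for" *S. stercoralis*) and its group sizes (the middle figures in "248, 120, and 101 for FDC-group and 248, 119 and 110 for FDCx3-group").

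The parallel sentence in protocol 9.2 has an additional clause. It assigns 95%, 100% and 80% to *S. stercoralis* for the three comparisons already named, and then gives hookworm "82%, and 80% to compare the CRs of hookworm respectively for ALB vs FDCx3 and FDC vs FDCx3 comparisons". Protocol Table 1 and SAP Table 3 carry the same assignment: 95%, 100% and 80% under *S. stercoralis*, and 82% and 80% under hookworm.

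**The concern.** The SAP sentence cannot be right as printed. It lists three powers in order against two comparisons, for a species in which the plan excludes the third. Taken in order, ALB vs FDCx3 for hookworm would have 95% power and FDC vs FDCx3 would have 100%. Against the same document's Table 3 (82% and 80%) these are 13 and 20 points too high.

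What is at stake is the accuracy of a stated design figure for a secondary efficacy endpoint that has its own sample size. SAP 3.5 also asks for the sample-size assumptions to be checked at the interim analysis. Someone starting from the sentence would put the chance of missing the planned 15.5-point difference at about 5%; by calculation it is about 20%.

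There is a smaller inconsistency within the tabulated hookworm pair. ALB and FDC are assumed to have the same cure rate and the same number of children, so each comparison with FDCx3 is the same calculation. The two printed powers nevertheless differ.

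**Working it through.** **Inputs**
- Alpha: "an overall significance level of 5% adjusted for multiple tests by Bonferroni's correction, 80% power and inflated for 10% lost-to-follow-up" (SAP 3.5). Table 3 shows the adjusted level as 0.0167, that is 0.05/3.
- Sidedness: "all tests will be two-sided" (SAP 5.7). The critical value at two-sided 0.05/3 is z = 2.394.
- Cure rates for ALB, FDC and FDCx3 (SAP 3.5): "79.5%, 79.5% and 95% for hookworm"; 45%, 79% and 94% for *S. stercoralis*; 23.7%, 43.7% and 59% for *T. trichiura*.
- Evaluable n before inflation (SAP Table 3, protocol Table 1): hookworm 91, 91, 99; *S. stercoralis* 42, 108, 107; *T. trichiura* 116, 223, 223.

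**Formula** (pooled normal approximation)

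Power = Φ[(|p2 − p1| − z·SE0) / SE1], where SE0 = √[p̄(1−p̄)(1/n1 + 1/n2)], SE1 = √[p1(1−p1)/n1 + p2(1−p2)/n2], and p̄ is the n-weighted mean cure rate. Neither document prints its formula, so the formula was first tested against the tabulated powers.

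**Step 1: reproduce the plan's figures for the other two species**

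| Comparison | Working | Calculated | Tables |
|---|---|---|---|
| *T. trichiura* ALB vs FDC | Φ(1.314) | 90.6% | 91% |
| *T. trichiura* ALB vs FDCx3 | Φ(4.206) | >99.9% | 100% |
| *T. trichiura* FDC vs FDCx3 | Φ(0.848) | 80.2% | 80% |
| *S. stercoralis* ALB vs FDC | (0.34 − 2.394×0.08374)/0.08619 = 1.619 | 94.7% | 95% |
| *S. stercoralis* ALB vs FDCx3 | (0.49 − 2.394×0.07258)/0.08012 = 3.947 | >99.9% | 100% |
| *S. stercoralis* FDC vs FDCx3 | (0.15 − 2.394×0.04666)/0.04542 = 0.843 | 80.0% | 80% |

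All six agree after rounding. The figures 95%, 100% and 80% are therefore the *S. stercoralis* powers.

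**Step 2: hookworm, either comparison with FDCx3**
- p̄ = (91×0.795 + 99×0.95)/190 = 166.395/190 = 0.8758
- SE0 = 0.0479; SE1 = 0.04765
- (0.155 − 2.394×0.0479)/0.04765 = 0.846, and Φ(0.846) = 80.1%

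This matches the tabulated 80% for FDC vs FDCx3. The tabulated 82% for ALB vs FDCx3 is 1.9 points above it.

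**Step 3: can any reasonable variant give 95% or 100% for hookworm?**

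| Variant (91 vs 99 unless stated) | Power |
|---|---|
| Continuity-corrected, two-sided 0.0167 | 73.4% |
| Unpooled variance, two-sided 0.0167 | 80.5% |
| Exact power of the chi-square test, two-sided 0.0167 | 82.9% |
| Arcsine, two-sided 0.0167 | 83.4% |
| Pooled, inflated n (101 vs 110), two-sided 0.0167 | 84.6% |
| Pooled, two-sided 0.025 (two comparisons) | 84.1% |
| Pooled, two-sided 0.05, no adjustment | 90.0% |
| Pooled, one-sided 0.05, no adjustment | 94.5% |

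Only an unadjusted one-sided test comes near 95%, and that contradicts the stated alpha and sidedness. No variant gives 100%. At the stated alpha, 95% would need about 143 vs 155 evaluable children.

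**Step 4: the 82%/80% pair**

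Both comparisons are 91 vs 99 at 79.5% vs 95%, so any single method must return one value. Raising the smaller group to 99 gives 81.6% with the pooled formula, which rounds to 82%. That is a possible origin of the 82%, but nothing in the documents confirms it.

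**The case against.** The error is editorial and exposes itself. Three powers cannot be matched in order to two comparisons, SAP 3.5 refers the reader to Table 3, and Table 3, protocol Table 1 and the protocol sentence all give hookworm 82% and 80%. The target of 80% power is stated consistently. This stands, and it limits the weight of the point.

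Some stronger readings are tempting but unsupported:
- A reader might infer that the SAP gives no power for *S. stercoralis*. Only the sentence lacks it; Table 3 gives all three values.
- A reader might infer that the SAP as a whole overstates hookworm power by 15 points, or that the species is underpowered. One sentence is wrong, the tables are not out by that amount, and the calculated power meets the 80% target.
- A reader might infer that a null hookworm result will be over-read. No analysis rule in the SAP uses the prospective power, and anyone interpreting the result would have the observed cure rates and Table 3.
- A reader might infer that the 82% is shown to be the mistaken cell. The formula is not printed, and exact chi-square power is 82.9%. The pooled formula that fits the other tabulated powers favours 80%, but the 82% may reflect a different n. What is certain is that the two entries should agree.

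It may also be said that a line was lost when the PDF was read. That cannot be fully excluded. However, the sentence runs on without a visible gap, and the missing words lie between two occurrences of the same phrase in the protocol, which fits a copying skip.

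**Conclusion.** The sentence in SAP 3.5 is wrong as printed: it gives hookworm the *S. stercoralis* powers and conflicts with SAP Table 3 and protocol 9.2. Calculated hookworm power is 80.1% for each of its two comparisons, about 15 points below the sentence's first figure and 20 below its second. This assumes the stated cure rates, the evaluable n, two-sided alpha 0.05/3 and the pooled formula. Other approximations at that alpha and n give 73.4% to 83.4%, so the conclusion does not depend on the choice.

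The 82%/80% pair is a minor second inconsistency of 2 points, certain in that the inputs are identical but not in which entry is at fault. Both points correct stated figures. Neither touches the sample sizes, the planned analyses or the design.

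**What to change.** In SAP 3.5, restore the clause from protocol 9.2: 95%, 100% and 80% for *S. stercoralis* in ALB vs FDC, ALB vs FDCx3 and FDC vs FDCx3, followed by the hookworm powers for ALB vs FDCx3 and FDC vs FDCx3 only.

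Check the 82%/80% pair against the original sample-size output and print one value for both hookworm comparisons in SAP 3.5, SAP Table 3, protocol Table 1 and the protocol 9.2 text. The pooled formula gives 80.1%. If the 82% came from a different n or method, say so and show the inputs. One line naming the power formula would settle the question for later readers.

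The cost is one sentence in the SAP and one figure in four places. Nothing needs to be recalculated for recruitment, and trial conduct is unaffected.
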